6.6. Subject Population

Form Revised as of 14 Apr 14

G:\60MDG\SGSE\4. SGSE - Clinical Research\IRB Folder\IRB\Templates
and Forms\Master Protocol Office Forms (Do not delete)\Human

Page 11 of 24

For Protocol Office use only:

Protocol title: NATO Litter: Fluid Immersion System
(FIS) versus Traditional Mattress for Pressure Dispersion
FDG20160005H wAmd5

(investigator names redacted 23 Jan 20)

DGMC Human Research Protocol

Age Range: ≥ 18 y/o Children (≤ 18)

Sex: Male Female

Vulnerable Population: No Yes (explain)

Number of Subjects:

- Total Number of Subjects (nation-wide/study-wide): 43
- Number of Subjects Planned for DGMC: 43
- Number of Subjects Planned for (Specify Institution): N/A

Statistical tests will be 2-tailed with a significance level of 0.05. A 25% attrition rate is expected. A total of 53 subjects will be recruited in order to obtain 43 evaluable subjects with complete data sets.

Inclusion/Exclusion Criteria:

Inclusion:

- Adults over the age of 18 years with lawful access to Travis AFB.

Exclusion:

- Orthopedic or neurological conditions that prevent a subject from lying flat (supine) without any pillows for head, neck, or lumbar support
- Medical conditions (such as an uncontrollable tremor or twitch) that prevent a subject from staying still for the required periods of time (20 minute increments).
- Pregnancy
- Inability to ambulate unassisted, unstable gait (presenting increased fall risk)
- Extremity prosthetics (hand/arm or foot/leg)
- Height greater than 72 inches (6 feet) - exceeds length of the litter & mattress surfaces
- Body weight greater than 300 lbs

For Protocol Office use only:

Protocol title: NATO Litter: Fluid Immersion System
(FIS) versus Traditional Mattress for Pressure Dispersion
FDG20160005H wAmd5

(investigator names redacted 23 Jan 20)

DGMC Human Research Protocol

- Subjects who find it difficult, uncomfortable or impossible to remain still for the necessary study time durations (20 minute increments) on the relatively narrow litter surfaces will be removed from the study.
- Subject does not speak or understand the English language

Recruitment:

1. **Fliers** – Will be posted throughout DGMC in approved/authorized locations such as Heart, Lung & Vascular, Family Medicine, Family Health, Internal Medicine and Flight Medicine clinics, cafeteria, elevators and other public areas. Advertisement posters/fliers will also be posted and briefed in other public buildings on Travis AFB in order to ensure recruitment of a sample representative of the active duty population. Research coordinators may also sit near advertisement posters in the clinic waiting room, common areas and cafeteria to answer any potential participant's questions.
2. **Pamphlets** – Will be placed in the waiting rooms of primary care clinics, base gym, Base Exchange (BX), hospital cafeteria and Grant Central Station.
3. **E-mail/Newspaper** – The research team may elect to advertise the study via e-mail sent out by Wing public affairs office. The research team may also elect to advertise via Air Force newspaper publications or other military newspapers at surrounding bases.
4. **Marquee** – Base and MDG

Consent:

Subjects that have expressed interest in the study will be scheduled for an informed consent review/initial visit at the Clinical Investigation Facility (CIF). The subject will be brought to a private exam room or office where they will be individually consented by the research coordinator, PI or other qualified research team member. The study team member will explain the nature and scope of this study, discuss potential risks and benefits of participation, answer questions and ensure the subject fully understands the informed consent document. The study will be explained to the subject in lay terms. At least one hour of study staff time will be set aside for each participant to receive information, ask questions and consider participation in the study. The subject may elect to discuss the study with others if they so choose, prior to agreeing to participate. If the subject agrees to participate, the IRB approved informed consent document will be signed and dated by the subject and primary investigator or another delegated research team member. A copy of the signed consent form will be made and provided to the subject. The original signed consent form will be turned into the protocol office and a copy will be placed in the subject's study folder. The study folder will be stored in a locked filing cabinet in an office that is locked when the office owner is not in the room. Subjects will be assured that they may withdraw from the study at any time for any reason and their medical treatment will not be

compromised. Research procedures will not start until the IRB approved informed consent document has been signed and dated by the subject and research team member.

6.7. Safeguards for Protecting Subjects:

- All subjects will be treated in compliance with AFI 40-402 and applicable FDA and DHHS guidelines.
- Subjects will be monitored by study staff members at all times while on a litter to reduce the risk of falling off the litter.
- Study staff members will observe and assist subjects as needed when getting on and off of the litter to reduce the subject's fall risk.
- A step stool will be available to assist subjects in safely getting onto and off of the litter.
- Subjects will be assigned an ID number after they are consented. This ID number will be used to protect subject privacy and ensure confidentiality of recorded data. Subject's protected health information will not be accessed or recorded during this research protocol.
- **Data Entry:** Data will be entered by authorized study personnel only. Upon completion of data entry all hard copy documents will be stored as per the hard copy records policy outlined below. All electronic data will be housed on the DGMC computer drive and will only be accessible via a Common Access Card enabled computer accessible only to study personnel within a secured office. All electronic transmissions of data will be encrypted over a secured network.
- **Data security and transfer:** Study documents will reside in the Clinical Investigation Facility within the 60MDG SGSE Directory in a limited access password protected directory designated exclusively to the study. Access will be granted only to study personnel.
- **AES Encryption:** To be in compliance with Government regulations study personnel will utilize 128 bit AES encryption. AES is widely used across the government healthcare sector to secure data-at-rest, data-in-motion and data-in-transit. All data transfers will be made via (password protected CD, encrypted Electronic Mail, Secured FTP server, etc.). All data files will utilize the Advanced Encryption Standard approved cryptographic algorithm used to protect electronic data.
- **Hard Copy Records:** A copy of the IRB approved informed consent signed and dated by the study subject and designee will be provided to the subject. The original signed and dated IRB approved informed consent form will be placed with other study records, in a locked cabinet and secured area within the IRB Protocol Office at the Clinical Investigation Facility. A copy of the records will be in the coordinators offices located in the Internal Medicine Clinic. These records will be accessible only to study personnel, the IRB, and employees of authorized Federal departments and regulatory agencies. Duplicates will be provided to the volunteer upon written request.

For Protocol Office use only:

Protocol title: NATO Litter: Fluid Immersion System
(FIS) versus Traditional Mattress for Pressure Dispersion
FDG20160005H wAmd5

(investigator names redacted 23 Jan 20)

DGMC Human Research Protocol

6.8. Data Collection/Analysis:

A sample size of 43 subjects is required for this study. This is similar to the sample size used by Col Elizabeth Bridges and colleagues in a study of skin interface pressure on a NATO litter³. In their study, a stratified sample (n= 32) with four support surfaces using a single canvas style NATO litter was used. The surface effect was statistically significant for all peak pressure and surface area analyses (repeated-measures analysis of variance, $p < 0.01$, $\alpha 0.05$, $\beta 0.20$). Interface pressure will be measured using XSensor X3 Pressure Mapping 32x 80 medical mattress, 5-50 & 10-200mmHg pressure range. The XSensor system uses force transducer arrays, which consist of a grid of transducers with half inch square resolution aligned in a matrix which is embedded in a 32 x 80 inch thin mat. This mat is placed under the subject to map their entire body. Calibration will be performed before and after each participant and the amount of drift evaluated. Mattress will be sanitized with disinfectant wipes between each participant.

A stratified sampling scheme will be used to ensure adequate representation of the following attributes: gender, normal weight and overweight or obese as determined by BMI.

The dependent variables (pressure mapping index = mmHg, Total body surface area (TSA) greater than 30 mmHg = cm²; transcutaneous oxygenation (tcpO₂) = mm Hg) will be measured on four different support surface combinations using the independent variables – litters/mattresses: (1) NATO litter with the WELP; (2) NATO litter with the Dolphin FIS; (3) Raven litter with the WELP and (4) Raven litter with the Dolphin FIS.

The subjects will service as their own controls. Baseline measures of tcpO₂ over bilateral scapular regions will be taken with the subjects sitting upright prior to having them lay supine on the support surfaces for pressure mapping with repeated tcpO₂ measurements.

Data collected will include the subject's age, race, gender, height and weight the weight will be measured on a calibrated scale.

Subject height and weight will used to determine their BMI.

BMI is an individual's weight (in kilograms) divided by their height squared (in centimeters). The BMI calculator or tables from the U.S. Department of Health and Human Services National Institutes of Health (NIH) web will be used to calculate BMI for this study.
http://www.nhlbi.nih.gov/health/educational/lose_wt/BMI/bmi_tbl.htm

NIH BMI Categories:

For the Purposes of this study: BMI

Underweight = <18.5

Normal weight = 18.5–24.9

Overweight = 25–29.9

Obesity = BMI of 30 or greater

Ideal = 18.5-24.9

High = 25 or greater

This is a cross-factor design that will use a Repeated Measures Analysis of Variance (ANOVA) model to examine the effects of within and between factors. Mean change in tcpO₂ (mmHg), LDP pressure units, surface area (cm²) will be computed. All analyses will be done using STATA v 13.0 (College Station, TX).

Source of Research Material per Participant:

| Source of Research Material per Participant | Standard Care | Research Driven |
|--|---------------|-----------------|
| Demographic Data | 0 | 1 |
| Age in years (89+ for anyone over 89 years of age) | 0 | 1 |
| Gender – Male or Female | 0 | 1 |
| Body Mass Index (BMI) | 0 | 1 |
| Height (centimeters/inches) | 0 | 1 |
| Weight (pounds/kilograms) | 0 | 1 |
| Pressure Mapping (mmHg) - NATO Litter (WELP) | 0 | 1 |
| Transcutaneous Oxygenation (TcPO ₂) mmHg | 0 | 4 |
| Pressure Mapping (mmHg) - NATO Litter (FIS) | 0 | 1 |
| Transcutaneous Oxygenation (TcPO ₂) mmHg | 0 | 4 |
| Pressure Mapping (mmHg) – Raven Litter (WELP) | 0 | 1 |
| Transcutaneous Oxygenation (TcPO ₂) mmHg | 0 | 4 |
| Pressure Mapping (mmHg) - Raven Litter (FIS) | 0 | 1 |
| Transcutaneous Oxygenation (TcPO ₂) mmHg | 0 | 4 |
| | | |
| | | |
| | | |
| | | |

7. Conflict of Interest

None

8. Investigation Schedule

Estimated Timeline: IRB approval estimated for May 2016. PI PCS'd and alternate deployed, therefore, anticipated protocol start date Jan 2018 protocol start (need additional equipment, supplies, also requesting additional funding).

| | Jan 2018 Y2Q2 | Y2 Q3 | Y2 Q3 | Y2 Q4 | Y3 Q1 | Y3 Q2 | Y3 Q3 | Y3 Q4 |
|-------------|------------------|-------|-------|-------|-------|-------|-------|-------|
| Recruitment | X | X | X | X | | | | |
| Enrollment | X | X | X | X | X | X | | |

For Protocol Office use only:

Protocol title: NATO Litter: Fluid Immersion System
(FIS) versus Traditional Mattress for Pressure Dispersion
FDG20160005H wAmd5

(investigator names redacted 23 Jan 20)

DGMC Human Research Protocol

| | | | | | | | | |
|----------------------|---|---|---|---|---|---|---|---|
| Data Collection | X | X | X | X | X | X | | |
| Statistical Analysis | | | | | | X | X | |
| Publications/Reports | | | | | | X | X | X |

9. Use of Investigational Drug(s) No Yes

10. Use of Investigational Device(s) No Yes

11. Support Required

CIF Support:

Administrative, bio-statistician consultation and Clinical Research Coordinator to help with subject recruitment, informed consent process and data collection support is required. (See attachments for Letter of Support).

Other Support:

DGMC Hyperbaric Clinic: Staff and equipment for Transcutaneous Oximetry (tcpO₂)
(see attachments for Letter of Support).

See attached Letters of Support

12. Budget, Equipment, and Supplies:

Requesting Funds: Yes No

R&D O&M HMJ OTHER (explain source):

| Study Year | Item Description | Unit of Issue (UOI) | Cost/UOI | Quantity | Total Cost |
|------------|--|---------------------|-----------|----------|------------|
| 2015 | Dolphin FIS | 1 | 19,470.00 | 1 | 19,470.00 |
| 2015 | X3 Sensor Sleeves | 100 | 150.00 | 1 | 150.00 |
| 2015 | NATO Litter NSN: 6530-01-380-7309 | 1 | 397.78 | 1 | 397.78 |
| 2015 | Litter Raven 90C NSN: 6530-01-432-5114 | 1 | 391.25 | 1 | 391.25 |
| 2015 | Litter Stands NSN: 6530-01-618-7419 | 1 pair | 778.00 | 2 | 1556.00 |
| 2015 | Mattress Litter | 1 | 320.00 | 1 | 320.00 |

For Protocol Office use only:

Protocol title: NATO Litter: Fluid Immersion System
(FIS) versus Traditional Mattress for Pressure Dispersion
FDG20160005H wAmd5

(investigator names redacted 23 Jan 20)

DGMC Human Research Protocol

| | | | | | |
|------|---|---|-----------|----|-----------|
| 2016 | Dell Laptop Computer | 1 | 3,368.39 | 1 | 3,368.39 |
| 2016 | XSENSOR X3 Pressure Mapping System | 1 | 12,650.75 | 1 | 12,650.75 |
| 2016 | Biopac® Laser Doppler package (includes: MP-160, LDF 100c, LDF Probe TSD 140) | 1 - MP-160 2 - LDF 100c 2 - LDF Probe TSD | 31,000 | 1 | 31,000 |
| 2016 | TCOM probes | 1 | 1,500 | 2 | 3,000 |
| 2016 | TCOM Fixation rings | 1 Box of 100 | 150.00 | 2 | 300.00 |
| 2016 | TCOM membrane | 1 Box of 12 | 132.31 | 10 | 1,323.10 |

I understand that the funding is the responsibility of the PI, which includes; management, tracking, recording and must be reported to the IRB annually with your continuation report.

13. Manpower

| Rank | AFSC | # hours duty time | # hours off-duty time |
|--------|---------|-------------------|-----------------------|
| Col | 46N3 | 80 | 40 |
| Lt Col | 46N3 | 240 | 40 |
| CRC | Civ/CTR | 80 | 0 |
| CRC | Civ/CTR | | 0 |
| CRN | CTR | 40 | 0 |
| CRN | CTR | 40 | 0 |
| RA | CTR | 80 | 0 |
| RA | CTR | 80 | 0 |

14. Institutional Official (IO)

(name redacted 23 Jan 20), Col, USAF, MC
Commander, 60th Medical Group

For Protocol Office use only:

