in a hostile and austere environment where care was focused primarily on immediate life-threatening interventions and medical evacuation to a higher level of care. Medical evacuation most likely occurred on a NATO field litter, which can produce peak interface pressures greater than 30 mm Hg over bony prominences³ and limit tissue perfusion³⁵. The combination of poly-trauma, traumatic brain injury, hypoperfusion, sedation, cervical collars, and medical evacuation places injured individuals at high risk for pressure ulcer development early in the care continuum. Finding ways to reduce or eliminate pressure ulcer development is a patient safety/quality of care issue. Interventions to help reduce/eliminate this problem as early in the continuum of care as possible would improve patient safety outcomes and raise quality of care. In the operational setting, that starts with the transport litter.

Purpose:

The purpose of this study is to measure peak skin interface pressures and the total area of the body exposed to skin interface pressures above 30 mm Hg while subjects are in the supine position. Two different support surfaces will be applied to a standard North Atlantic Treaty Organization (NATO) litter (NSN: 6530-01-380-7309) and a Raven 90C Litter (NSN6530-01-432-5114). The support surfaces are the Warrior Evacuation Litter Pad (WELP) and the Dolphin Fluid Immersion System (FIS). These pressure measurements along with transcutaneous oxygenation readings will allow us to determine differences between support surfaces.

This research protocol has one major aim:

To determine the difference in the pressure redistribution qualities between the WELP and the Dolphin FIS

There are also two secondary aims:

1. To determine the difference in the pressure redistribution qualities of the WELP when used as the mattress on the NATO litter and Raven litter.
2. To determine the difference in the pressure redistribution qualities of the Dolphin FIS when used as the mattress on the NATO litter and Raven litter.

6.3. Hypotheses or Research Questions or Objectives:

Research Questions:

1. Is there a significant difference in pressure redistribution qualities between the WELP and Dolphin FIS mattresses on the NATO Litter?
2. Is there a significant difference in the pressure redistribution qualities between the WELP and Dolphin FIS mattresses on the Raven Litter?

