3. Is there a significant difference in the pressure redistribution qualities of the WELP between the NATO and Raven 90C litters?

4. Is there a significant difference in the pressure redistribution qualities of the Dolphin FIS mattress between the NATO and Raven litters?

Hypotheses:

1. Pressure redistribution qualities will be greater for subjects on the Dolphin FIS than the WELP in the supine position.

2. There is a difference in pressure distribution between men and women, given BMI level (high, ideal) for subjects on the WELP padded NATO with Raven litters.

3. There is a difference in pressure distribution between men and women, given BMI level (high, ideal) for subjects on the Dolphin FIS padded NATO with Raven litters.

4. There is a difference in pressure redistribution qualities of the WELP for subjects on the NATO and Raven litters.

5. There is a difference in pressure redistribution qualities of the Dolphin FIS for subjects on the NATO and Raven litters.

Outcome measures:

Pressure Redistribution: Peak Pressure Index & Total Surface Area (TSA)

Pressure redistribution qualities will be measured in mmHg using XSensor X3 pressure mapping technology. To minimize the risk of a faulty sensor or false reading over one sensor, the average of eight cells around the region will be recorded and referred to as the Peak Pressure Index (PPI). Peak interface pressure is the highest average pressure (mm Hg) measured over vulnerable bony prominences (occiput, sacrum, and bilateral scapula, buttocks, and heels).

TSA will be measured in centimeters squared (cm²). Vulnerable bony prominences with skin interface pressures exceeding 30 mm Hg will be documented.

Tissue Perfusion: Transcutaneous Oxygenation:

Transcutaneous partial pressures of oxygen (tcpO₂) in millimeters of mercury (mmHg) is non-invasive measurement/monitoring of the skin's surface partial pressure of oxygen. For purposes of this study, tcpO₂ measurements will be captured in the scapula region and expressed in mm Hg. Transcutaneous tissue perfusion has been used as the index of tissue viability by several groups^{44,45,49}. From the early work of Seiler et al. (1997, 1983)^{47,48}, a baseline tcpO₂ value for

For Protocol Office use only:

Protocol title: NATO Litter: Fluid Immersion System
(FIS) versus Traditional Mattress for Pressure Dispersion
FDG20160005H wAmd5

(investigator names redacted 23 Jan 20)

DGMC Human Research Protocol

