5.4.4.2. A mattress pad is recommended to prevent skin breakdown."

After the subject is positioned comfortably on the litter, the pressure mapping will begin. The peak interface pressure (the highest average pressure (mm Hg) measured over each

For Protocol Office use only:

Protocol title: NATO Litter: Fluid Immersion System
(FIS) versus Traditional Mattress for Pressure Dispersion
FDG20160005H wAmd5

(investigator names redacted 23 Jan 20)

DGMC Human Research Protocol

body region) will be measured for the occiput, sacrum, bilateral scapula, buttocks and heel areas. The total body surface area exposed to skin interface pressure greater than 30mm Hg will also be measured in centimeters squared (cm²) for each body region. Measures of tissue perfusion using the tcpO₂ in mmHg will be measured for comparison to baseline data. This process will take approximately twenty minutes for each of the four iterations. An additional 30 minutes is required to change the litter and mattress configurations. After baseline data are captured and tcpO₂ measurements are taken with the subject supine on all four litter/mattress combinations, the session is complete. Data from subjects who do not complete all four litter/mattress combinations will be excluded from the analysis. An estimated 25% attrition rate is factored into this study to ensure that 43 completed data sets are obtained.

6.5. Risks/Benefits:

- There is a potential risk of injury from falling off the litter while attempting to mount or dismount. This risk will be minimized by having a member of the research staff present whenever a subject is on the litter. Staff will be available to assist participants on and off the litter. A step stool will also be available to assist participants in safely mounting and dismounting the litter.
- There is also a potential risk of skin reaction to the adhesive which will hold the transcutaneous oxygenation transducers in place. If a participant shows signs and/or symptoms of skin irritation from the adhesive (redness, itching, rash or hives), the adhesive will be removed and the participant will be encouraged to see their primary care provider if the signs and/or symptoms do not quickly resolve or becomes worse after the adhesive is removed. If the participant's initial reaction to the adhesive pads is severe (difficulty breathing, face/lips, throat swelling, loss of consciousness) the subject will be taken to the DGMC Emergency Department for treatment.

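### The major aim (WELP versus Dolphin FIS) has no deciding endpoint or decision rule, so the error rate of Hypothesis 1 is undefined

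*Combined protocol and SAP*

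**What the plan says.** - **Aim (section 6.2, Purpose).** The single major aim is "To determine the difference in the pressure redistribution qualities between the WELP and the Dolphin FIS". The two litter comparisons are secondary aims.
- **Questions and hypothesis (section 6.3).** Research Question 1 asks: "Is there a significant difference in pressure redistribution qualities between the WELP and Dolphin FIS mattresses on the NATO Litter". Research Question 2 asks the same on the Raven litter. Hypothesis 1 makes one directional claim that is not split by litter: "Pressure redistribution qualities will be greater for subjects on the Dolphin FIS than the WELP in the supine position".
- **Outcomes (section 6.3).** The construct is defined under the heading "Pressure Redistribution: Peak Pressure Index & Total Surface Area (TSA", and neither measure is ranked above the other. Transcutaneous oxygen (tcpO₂) has its own heading, "Tissue Perfusion: Transcutaneous Oxygenation". It is a separate outcome and is not counted below as a measure of the major aim.
- **Recording (section 6.4).** Peak pressure "will be measured for the occiput, sacrum, bilateral scapula, buttocks and heel areas", and area above 30 mmHg is likewise recorded for each region. That is five regions, or eight sites if left and right are kept apart.
- **Analysis (sections 6.6 and 6.8).** Section 6.8 names a repeated-measures ANOVA with within and between factors, applied to two mattresses crossed with two litters. Section 6.6 sets the error rule: "Statistical tests will be 2-tailed with a significance level of 0.05". Neither section names a primary measure, a deciding effect, a role for body site in the model, a test order or a multiplicity method.

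**The concern.** A major aim needs a result that settles it. Here several results could: PPI or TSA, at one region, at several, or in a summary. The plan ranks its aims, but the choice lies inside the major aim, so that ranking does not remove it.

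Mixed results are plausible. FIS might lower sacral pressure but raise heel pressure, or improve PPI and not TSA. The plan does not say whether Hypothesis 1 would then be supported. Testing everything at 0.05, as written, leaves room to claim it on whichever result is significant. The study is meant to inform whether FIS is useful and feasible as a litter surface, so this affects the headline conclusion.

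**Working it through.** **No figure of the plan to reproduce.** The plan states no familywise error rate, and gives no effect size, standard deviation or power for its own sample size. The check asks what the stated 0.05 implies under each decision rule that the text leaves open.

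**Inputs from the protocol**
- α = 0.05, two-sided, per test (section 6.6).
- Measures of the construct: 2 (section 6.3).
- Body regions: 5 (section 6.4).
- Completers: n = 43 (sections 6.6 and 6.8).

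**Inputs assumed, because the protocol gives none**
- One common correlation ρ between test statistics, shown at 0, 0.5, 0.7 and 0.9.
- The number m of tests that could support Hypothesis 1.

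**Rule A: any one significant result counts, with no true difference.** For ρ = 0, the chance of at least one false result is 1 − 0.95^m:
- m = 2: 1 − 0.95² = 1 − 0.9025 = 9.75%
- m = 10: 1 − 0.95¹⁰ = 40.1%

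For ρ > 0, write each statistic as √ρ·Z + √(1−ρ)·E, with Z and the E independent standard normal, and let c = 1.96. The chance is 1 minus the average over Z of [Φ((c − √ρZ)/√(1−ρ)) − Φ((−c − √ρZ)/√(1−ρ))]^m.

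| Tests that could support the claim | ρ = 0 | 0.5 | 0.7 | 0.9 |
|---|---|---|---|---|
| 2 (PPI and TSA, one summary each) | 9.8% | 9.1% | 8.4% | 7.0% |
| 10 (2 measures × 5 regions, tested separately) | 40% | 29% | 21% | 13% |

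A simulation of paired t tests with n = 43 (20,000 trials) agrees: 9.6%, 9.2%, 8.1% and 6.8% for m = 2, and 40.2%, 29.3%, 22.1% and 12.9% for m = 10. All readings come from one body in one session, so the correlated columns are the more plausible.

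These figures count false differences in either direction. Counting only those that favour FIS, where a single test has 2.5%, m = 2 gives 4.9% to 3.5% and m = 10 gives 22% to 6.4% (ρ from 0 to 0.9).

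**Rule B: both measures must be significant.** The chance that both are falsely significant is 0.05 + 0.05 − (chance of at least one).
- ρ = 0: 0.10 − 0.0975 = 0.25%
- ρ = 0.9: 0.10 − 0.0704 = 3.0%

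This is below 5% throughout.

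**Rule C: one prespecified test.** The error rate is 5% by construction. In a simulation of two measures on two litters (40,000 trials), one prespecified measure averaged over the litters gave 5.0% to 5.1% at every correlation tried.

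**What 43 completers can detect (paired t test, noncentral t, 80% power)**
- One test at 0.05: standardised paired difference d = 0.44.
- First Holm step with ten other contrasts, 0.05/10 = 0.005: d = 0.58. Ten is the count if one region-level pressure contrast is primary (nine others remain) and tcpO₂ is averaged over the two sides.
- If whole-body area is primary and all ten regional contrasts plus tcpO₂ are kept, 0.05/11 gives d = 0.59.

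**The case against.** The strongest reply is that the design already points to an answer. The four surfaces form a complete two-by-two of mattress and litter, the model is a cross-factor repeated-measures ANOVA, and neither the major aim nor Hypothesis 1 is split by litter. The natural deciding effect is the mattress main effect, with Research Questions 1 and 2 as follow-up on each litter. This stands as far as it goes. It is why the two litters are not counted above as extra chances to claim Hypothesis 1. But the plan does not call that effect decisive, and it would still leave two measures and the regions open.

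A second reply is that recording by region is not a plan to test by region. Sections 6.2 and 6.8 speak of a total area, and site could enter the ANOVA as a within-subject factor. This also stands. The ten-test row is conditional, and the two-measure row is the only one that needs no assumption about separate site tests.

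A reader might infer that the type I error of the major aim is definitely inflated, perhaps to 56% (eight sites × two measures = 16 independent tests) or higher by litter. The documents do not support that. Inflation needs an any-one rule, which the text neither states nor excludes. The larger figures also need separate site or litter tests and zero correlation.

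A reader might also take the undefined LDP pressure units in section 6.8 as one more unplanned endpoint. That sentence says what will be computed, not clearly what will be tested. The mismatch with the list of dependent variables is a separate drafting point and adds nothing to the error-rate argument.

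**Conclusion.** The point holds as an undefined decision rule, not as a demonstrated inflation. The major aim rests on two unranked measures recorded by region, each test is at two-sided 0.05, and nothing says which result settles Hypothesis 1.

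Depending on the rule adopted, the chance of a false mattress difference runs from under 5% (both measures required) to 7.0% to 9.8% (either measure), or 13% to 40% (any of ten regional results). The ranges rest on an assumed common correlation of 0.9 down to 0, and the last also on separate regional tests. The absence of a deciding result does not depend on any of these assumptions.

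The sponsor should correct this before analysis. The data stay usable whichever way it is resolved.

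**What to change.** Amend protocol sections 6.6 and 6.8 before analysis:

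1. State that Hypothesis 1 is decided by one test at two-sided 0.05: the FIS minus WELP mattress main effect over both litters, from the planned repeated-measures ANOVA, on one endpoint already collected (for example, total area above 30 mmHg).
2. Report the mattress-by-litter interaction and the two litter-specific contrasts with 95% confidence intervals, to answer Research Questions 1 and 2.
3. Say how body site enters: as a within-subject factor, as a summary, or as separate analyses.
4. Report the remaining PPI, TSA and tcpO₂ mattress contrasts as descriptive with 95% confidence intervals. If any are to be confirmatory, adjust them by Holm's method.

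**Cost.** This is a change of protocol wording and needs no new data or subjects. The non-primary results lose confirmatory status or face a stricter threshold: the detectable standardised difference rises from 0.44 for the primary test to about 0.58 at a first Holm step of 0.05/10. The main effect over litters is also harder to interpret if the interaction is large, which is why step 2 reports both litters.

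### The attrition figures do not agree: 53 recruited at 25% attrition yields about 40 complete data sets, not 43, and reaching 43 would need 58 recruited.

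*Combined protocol and SAP*

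**What the plan says.** The figures appear in three sections of the combined protocol and SAP.

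- **Section 6.6 (Subject Population)** gives the rate, "A 25% attrition rate is expected", and then the recruitment number, "A total of 53 subjects will be recruited in order to obtain 43 evaluable subjects with complete data sets". The form entries above these sentences read "Total Number of Subjects (nation-wide/study-wide): 43" and "Number of Subjects Planned for DGMC: 43", without saying whether 43 counts subjects recruited or subjects evaluable.
- **Section 6.4 (Research Design and Methods)** repeats the rate and the target: "An estimated 25% attrition rate is factored into this study to ensure that 43 completed data sets are obtained". It also defines who is analysed: "Data from subjects who do not complete all four litter/mattress combinations will be excluded from the analysis".
- **Section 6.8 (Data Collection/Analysis)** sets the target: "A sample size of 43 subjects is required for this study". The support given is similarity to an earlier litter study: "In their study, a stratified sample (n= 32) with four support surfaces using a single canvas style NATO litter was used".

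**The concern.** An attrition rate is a share of those who enter. On that reading, the rate, the recruitment number and the target are inconsistent: any two of them fix the third, and the stated third does not match.

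Incomplete subjects are removed from the analysis altogether, so attrition reduces the analysed number one for one. No section provides for replacing dropouts or for recruiting beyond 53. The plan calls 43 a requirement and presents the allowance as securing it, yet on its own figures it should expect to miss. The unlabelled 43 on the form adds to the uncertainty, because a reader of the form alone would take it as the number to be enrolled.

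**Working it through.** **Inputs**

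- Attrition rate d = 25% (6.4 and 6.6)
- Number recruited = 53 (6.6)
- Target complete data sets = 43 (6.4, 6.6 and 6.8)
- Only subjects who complete all four combinations are analysed (6.4)

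**Reproducing the plan's 53**

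- The valid inflation is N / (1 − d) = 43 / 0.75 = 57.33, rounded up to 58. This does not give 53.
- Adding the rate to the target gives N × (1 + d) = 43 × 1.25 = 53.75, which is 53 if truncated. This is the likely source, but the documents do not say so.
- Adding 25% protects only against attrition of 1 − 1/1.25 = 20%. Rounding up to 54 would not repair it: 54 × 0.75 = 40.5.

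**Checking each pair of figures against the third**

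- Keep 53 and 25%: 53 × 0.75 = 39.75 complete sets. The shortfall is 43 − 39.75 = 3.25, and 3.25 / 43 = 7.6%.
- Keep 43 and 25%: 58 recruited, since 58 × 0.75 = 43.5.
- Keep 53 and 43: attrition must be (53 − 43) / 53 = 18.9%, about 19%.

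**Chance of reaching 43**

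The documents give only a rate. Assuming that subjects complete independently with the same probability, the number completing is binomial:

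| Recruited | Attrition | Expected complete | P(at least 43) |
|---|---|---|---|
| 53 | 25% | 39.75 | 0.19 |
| 58 | 25% | 43.5 | 0.63 |
| 53 | 19% | 42.93 | 0.57 |

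For 53 recruited at 25% attrition, the central 95% range is 33 to 46 complete sets.

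**Effect on precision**

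The plan gives no effect size, standard deviation or power calculation for 43, so absolute power cannot be computed. The relative loss can be gauged. Standard errors scale with 1/√n, and √(43/40) = 1.037, so about 40 instead of 43 widens intervals by about 3.7%. As an illustration only, under a normal approximation, if 43 gave 80% power then 40 would give about 77%, and if 43 gave 90% then 40 would give about 88%.

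**The case against.** The strongest reply is that the mismatch is real but hardly matters. The target of 43 has no power calculation behind it, only resemblance to a study of 32 subjects. Each subject serves as their own control on four surfaces, and 40 instead of 43 costs under 4% in interval width. That stands. It limits the weight of the point but does not make the figures agree.

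A second reply is that the authors meant to recruit a quarter more than the target, so the fault lies in calling that margin an attrition rate. This may well be how 53 arose. The ratio 10/43 = 23.3% does not count against it, because truncating 53.75 produces exactly that. But the text calls 25% an expected attrition rate in two sections and nowhere defines it as a margin on completers. If a margin was meant, the sentences are still wrong as written.

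A third reply concerns the probabilities. Plans are commonly sized to the expected yield, and recruiting 58 does just that, so a chance of 0.57 to 0.63 is no defect in itself. This is fair: the mismatch in expected values is sufficient, and the probabilities bear only on the promise that 43 will be secured.

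Finally, the form's 43 is a labelling matter, which the sentences below it partly clear up. It is not evidence of the arithmetic error, though it belongs in the same correction.

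**Conclusion.** The concern holds. At the stated 25% attrition, 53 recruits yield an expected 39.75 complete data sets, which is 3.25 (7.6%) below the 43 that section 6.8 calls for; 43 would need 58 recruits. This rests only on the plan's own three figures and on reading attrition as a share of those recruited. The probability of 0.19 of reaching 43 also assumes independent completion. The practical effect is modest, about 3.7% on interval width, and the expected yield stays above the 32 of the study used for support. The sample-size statement should be corrected because it is wrong as written and cheap to put right.

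**What to change.** Choose one consistent set of numbers and carry it through every place they appear.

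- **Option A: keep 53 and 25%.** In 6.4 and 6.6, state that about 40 complete data sets are expected from 53 recruited. In 6.8, replace the requirement of 43 with the same expected yield. On the form in 6.6, change both entries of 43 to 53, labelled as recruited, or to about 40, labelled as evaluable, using the same choice for both. This adds no subjects, but it gives up the plan's only stated target, so the sponsor should be content with about 40.
- **Option B: keep 53 and 43.** Restate attrition as about 19% in 6.4 and 6.6 and give the basis for it; the documents offer none at present. In 6.4, say that 43 complete sets are expected, not ensured. Label the form's two entries as evaluable. This adds no subjects.
- **Option C: keep 43 and 25%.** Change 53 to 58 in 6.6, make the same change from ensured to expected in 6.4, and label the form's entries as evaluable. This is the only option that keeps both of the plan's stated inputs. It adds five healthy volunteers.

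Under B and C, the target of 43 in 6.8 stands. The cost is a few sentences and two form entries, plus the five extra volunteers if C is chosen.
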